#### **10.3.5 Analysis of Secondary Efficacy Endpoints**

The analysis of the secondary efficacy endpoints will be conducted using data from the Full Analysis set.

Burden of disease will be analyzed in a way similar to the analysis of the best ORR (described in the previous section).

DOR will be summarized for responders (*i.e.*, subjects with CR or PR only) by disease and cohort. PFS and OS will be summarized by disease and cohort. The PFS rate at additional time points may also be evaluated (e.g., 26, 39 and 52 weeks). DOR, and PFS, will be obtained by using the Kaplan-Meier approach similar to OS described in the previous section.

Details of the analysis of secondary efficacy endpoints will be described in the Statistical Analysis Plans.

#### **10.3.6 Futility Analysis**

A non-binding futility analysis is planned for each cohort when 12 subjects have at least 2 evaluable tumor response evaluations after starting therapy. This analysis is designed to give a timely preliminary signal of response to consider along with cohort safety data to assess the advisability of continuing to enroll the cohort. Reported probabilities are based on exact calculations. There is a 54% chance that a result of 0 responses is observed when the true response rate is 5%. When the response rate in the population is the target rate of interest (15%); the chance of 0 responses is 14%, 1 response 30%, and 1 or more responses 96%. Therefore, observing 1 or more responses at the interim analysis would be supportive of further enrollment.

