In a Phase 2 SCR001-002 (TRINITY) study in patients with SCLC recurrent after at least two systemic chemotherapy regimens, rovalpituzumab tesirine dosed at 0.3 mg/kg every 6 weeks for two cycles (with an option for additional two cycles upon progression occurring  $\geq 12$  weeks after the second dose) had shown confirmed objective response rate of 16%, progression-free survival of 3.9 months and overall survival of 5.6 months in 3rd line DLL3High patients. Of note, prolonged stable disease with target lesion size reduction has been observed in a considerable number of patients receiving additional post-progression cycles of rovalpituzumab tesirine. Drug related grade 3 or above treatment emergent adverse events that occurred in at least 10 subjects include thrombocytopenia (11%), photosensitivity reactions (7%), anemia (4%), fatigue (4%),

and pleural effusion (4%). Adverse events leading to study treatment discontinuation occurred in 7% of subjects (AbbVie Stemcentrx, data on file).

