## **6.4 End-of-Treatment Visit**

The EOT visit occurs 42  $\pm$ 3 days after the last dose of study drug or within 7 days of documentation of the decision to discontinue treatment, whichever is later.

- Physical examination ([Section 7.2.1](#))
- Vital signs ([Section 7.2.2](#))
- PRO questionnaires EORTC QLQ-C30 and EQ-5D-5L – for subjects in Part B of the study only; to occur at screening, Cycle 2 (Days 1 and 29), and EOT ([Section 7.3.2](#))
- CBC ([Section 7.2.3](#))
- Serum chemistries ([Section 7.2.3](#))

- Coagulation tests (Section 7.2.3)
- Urinalysis (Section 7.2.3)
- Pregnancy test (Section 7.2.9) for women of child-bearing potential
- ECG in triplicate (Section 7.2.4)
- ECHO (Section 7.2.5) – The EOT ECHO should be conducted on EOT ( $\pm 3$  days) (Appendix 13.1).
- ECOG performance status (Appendix 13.3)
- Fluid retention questionnaire (Section 7.2.7)
- Disease assessment consisting of CT scans of the chest, abdomen, and pelvis (and neck if indicated) – may be omitted if a Disease/Response Assessment was performed within the last 6 weeks (Section 7.3)
- MRI of the brain – if clinically indicated (e.g., if CNS progression has been documented previously); may be omitted if a Disease/Response Assessment was performed within the last 6 weeks. CT of the brain with intravenous contrast may be substituted at the discretion of the Investigator.
- Blood sample for PK
- Blood sample for ATA
- (Optional) fresh tumor tissue, collected at PD (Section 7.3)
- Blood inflammatory markers (Section 7.5.2)
- Blood tumor markers (Section 7.5.3)
- Soluble biomarkers (Section 7.5.4)
- CTCs (Section 7.5.5)
- Prostate cancer subjects only: 99mTc Bone Scintigraphy – may be omitted if performed within the last 6 weeks (Section 7.3)

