### **6.5 Long-Term Follow-up (LTFU; Every 6 to 12 Weeks $\pm 1$ Week)**

For all subjects without PD (including those who discontinue study treatment for reasons other than PD), the first follow-up visit will occur at 6 weeks ( $\pm 1$  week) after the last dose of study drug, then every 6 weeks ( $\pm 1$  week) until 6 months, then every 12 weeks ( $\pm 1$  week), consisting of:

- Disease assessment consisting of CT scans of the chest, abdomen, and pelvis (and neck if indicated; Section 7.3)
- MRI of the brain – if clinically indicated (e.g., if CNS progression has been documented previously). CT of the brain with intravenous contrast may be substituted at the discretion of the Investigator.
- Blood tumor markers (Section 7.5.3)
- Circulating tumor cells (Section 7.5.5)

- Prostate cancer subjects only: 99mTc Bone Scintigraphy ([Section 7.3](#))
- Survival status

At progression, an optional collection of fresh tumor tissue may be conducted ([Section 7.3](#)).

After PD, subjects who are not retreated will be followed for subsequent anticancer therapies and dates, as well as survival status, similarly every 6 weeks ( $\pm 1$  week) until 6 months, then every 12 weeks ( $\pm 1$  week).

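### The futility look in Section 10.3.6 waits for 12 subjects with two evaluable scans, so it comes after more than 12 treated subjects and its chance of 0 responses at a true 5% rate is below the stated 54%

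*Combined protocol and SAP*

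**What the plan says.** The look is timed in Section 10.3.6: "A non-binding futility analysis is planned for each cohort when 12 subjects have at least 2 evaluable tumor response evaluations after starting therapy". The section gives a 54% chance of 0 responses when the true rate is 5%. For a true rate of 15% it says that "the chance of 0 responses is 14%, 1 response 30%, and 1 or more responses 96" per cent, and it concludes that "observing 1 or more responses at the interim analysis would be supportive of further enrollment". It does not say which subjects enter the count, or how a subject who progresses or dies before a second scan is handled.

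Other sections bear on this:

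- **Rates.** Section 10.1 uses 5% and 15% for cohorts of about 25 subjects treated at the recommended dose. Section 10.3.4 defines the response rate as a proportion of subjects and sets no two-scan requirement.
- **Response.** Section 7.3 requires two consecutive assessments of PR or CR.
- **Scans.** Section 6.3.7 sets scans every 6 weeks from Cycle 1 Day 1, so the second falls at about week 12.
- **After stopping.** The end-of-treatment CT "may be omitted if a Disease/Response Assessment was performed within the last 6 weeks" (Section 6.4). Scheduled follow-up scans are for subjects without progression: "For all subjects without PD (including those who discontinue study treatment for reasons other than PD), the first follow-up visit will occur" (Section 6.5).

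**The concern.** The two-scan condition does not fall evenly on responders and non-responders. A confirmed responder has at least two evaluations by definition. A subject whose first scan shows progression and who then stops treatment will often have only one, and a subject who dies before week 12 will have one or none. Those lost are all non-responders.

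The quoted probabilities are those for 12 subjects at a rate that applies to everyone treated. If some treated subjects never reach two scans, reaching 12 who do takes more than 12 treated subjects. An ineffective cohort is then less likely to show 0 responses than the plan says, and the look comes later, when more of the planned 25 or so have already been treated.

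**Working it through.** **Inputs.** n = 12 and rates p = 5% and 15% (Section 10.3.6). Confirmed responders always have two evaluations (Section 7.3). Let d be the share of treated subjects who never reach two evaluable scans. The documents give no value for d; 10% to 40% is an assumed range.

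**Step 1: the plan's own figures.**

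- P(0 of 12 at 5%) = 0.95^12 = 0.540. The stated 54% is reproduced.
- P(0 of 12 at 15%) = 0.85^12 = 0.142. The stated 14% is reproduced.
- P(1 of 12 at 15%) = 12 × 0.15 × 0.85^11 = 0.301. The stated 30% is reproduced.
- P(1 or more of 12 at 15%) = 1 − 0.85^12 = 0.858. The stated 96% is not reproduced, and it also conflicts with the section's own 14% for 0 responses.

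**Step 2: allow for subjects who do not reach two scans.** No responder is lost, so the response rate among two-scan subjects is p/(1 − d) and P(0) = (1 − p/(1 − d))^12. About 12/(1 − d) subjects have been treated when the condition is met.

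| d (assumed) | Treated at the look | P(0), true 5% | P(0), true 15% |
|---|---|---|---|
| 0% | 12 | 54.0% | 14.2% |
| 10% | 13.3 | 50.4% | 11.2% |
| 20% | 15.0 | 46.1% | 8.3% |
| 30% | 17.1 | 41.1% | 5.5% |
| 40% | 20.0 | 35.2% | 3.2% |

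A simulation at d = 20% gave 46.2% and 8.3%. The fall at a true 5% exceeds 2 percentage points once d is about 6%.

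**Step 3: read the 12 as a trigger only, and count everyone treated so far.** Then P(0) is roughly (1 − p)^(12/(1 − d)). At a true 5% this is 50.5%, 46.3%, 41.5% and 35.9% for d = 10%, 20%, 30% and 40%. The result is nearly the same, so the point does not depend on which reading is meant.

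**Step 4: one illustration of d.** Section 1.2 reports, for third-line DLL3-high SCLC, "progression-free survival of 3.9 months and overall survival of 5.6 months". If 3.9 months is taken as the median of an exponential distribution, the share progressing by week 6 (1.38 months) is 1 − exp(−ln 2 × 1.38/3.9) = 22%. With d = 22%, P(0) is (1 − 0.05/0.78)^12 = 45% at a true 5%, and 8% at a true 15%. This is an illustration only, because the study excludes SCLC.

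**The case against.** Several points on the other side stand.

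- **The text sets a time, not a denominator.** A reader might infer that only the 12 are counted and that an early progressor can never be among them. The documents do not say so. Section 7.3.1 permits treatment beyond progression, Section 5.4.2.1 lets treatment resume after isolated CNS progression, and the bone-lesion guidance in Appendix 13.7.1 requires a confirmatory scan when new lesions appear at the first reassessment. The end-of-treatment CT may be skipped but need not be. All of these lower d.
- **54% is not an arithmetic error.** It is exact for 12 subjects at 5%, and would be right if 5% meant the rate among two-scan subjects. Section 10.3.6 does not rule that out, but it speaks of the rate in the population, and Sections 10.1 and 10.3.4 point to treated subjects.
- **No responses are created.** A reader might infer that leaving out early failures inflates the response count. It does not: the rule is 0 against 1 or more, and the responders are the same. The effect is mainly that of looking after about 12/(1 − d) treated subjects, as Step 3 shows.
- **The size is unknown.** The cohorts differ widely; for medullary thyroid cancer, Section 1.3.2 describes benefit of about 12–24 months on frontline kinase inhibitors. The SCLC figure cannot be carried over to them.
- **The look is non-binding.** It is weighed with safety data, the sponsor may close a cohort at its discretion (Section 11.6), and the same shift makes a wrong flag at a true 15% less likely.

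These points limit the size and the consequence. They do not restore the 54%: under either reading, with 5% as the rate in treated subjects, any d above zero puts the chance below it.

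**Conclusion.** The concern holds as a misstated operating characteristic and a later look. It is not a bias in the final response rate, which this look does not alter.

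The chance of 0 responses at a true 5% lies below 54%: about 50% if 10% of treated subjects never reach two scans, and 35% if 40% do not. At a true 15% it lies below 14%, at about 11% and 3% for the same shares. The direction rests on two things: the 5% and 15% rates refer to treated subjects, and only non-responders are lost. The size rests on d, which the documents do not give. Some loss is plausible, since Section 4.1 asks for a life expectancy of only 12 weeks, about the time of the second scan.

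The calculation also takes each subject's response status as settled at the look. Section 10.3.6 does not say how a PR first seen at the second scan, and not yet confirmed, would be counted.

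The 96% is a separate error that needs no assumption: 12 subjects at 15% give 86%. It should be corrected because the section's closing inference follows directly from it. With n = 20 the figure would be 96.1%, but the documents do not show where 96% came from.

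**What to change.** In Section 10.3.6, define the look set as the first 12 treated subjects in the cohort, in order of first dose. Hold the look when each of them has either completed two post-baseline evaluations or has earlier progressed, died or stopped assessment. Count the latter as non-responders unless a response is confirmed. Fixing the 12 by order of dosing matters: taking the first 12 to reach an outcome would over-represent early failures. The stated 54%, 14% and 30% then apply, given settled response status. In the same edit, change the 96% for 1 or more responses at a true 15% to 86%.

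The cost is a sentence and one corrected figure, with no added visits or subjects, and the look comes earlier. The downside is that the chance of 0 of 12 at a true 15% returns to the stated 14%, and the look rests on somewhat fewer treated subjects. If the sponsor prefers to keep the present trigger, the alternative is to state the counted set and an assumed d, and to quote the probabilities that follow from them.

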### 10.1 Determination of Sample Size

Up to approximately 318 subjects are expected to participate in this two-part trial.

In Part A, up to approximately 144 subjects may be enrolled, assuming 3 dose-escalation cohorts of 6 subjects each (18 subjects) across 8 disease cohorts. The exact number will depend on the number of cohorts required to reach the MTD in each disease, and the number of subjects enrolled in each disease-specific cohort.

In Part B, up to approximately 174 subjects may be enrolled, including approximately 19 subjects in each of the 5 disease-specific cohorts. The rationale for the sample size is based on the assumption that an ORR of around 15% would be indicative of efficacy worthy of further investigation given the advanced cancers and extensive treatment history in this study population. Additionally, an ORR below 5% would provide evidence of an ineffective treatment. The goal of the efficacy analyses is to provide a preliminary signal that the response rate may potentially be within that target range.

When Part B is enrolled, each disease-specific cohort will have approximately 25 subjects treated at the RP2D, including the Part A and Part B subjects. [Table 10-1](#) presents the 90% two-tailed lower exact confidence limits for selected response rates.

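### Section 10.3.6 does not limit the 12 subjects of the futility look to the regimen being expanded, so its stated 14% chance of 0 responses need not apply to that regimen

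*Combined protocol and SAP*

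**What the plan says.** Section 10.3.6 sets the timing of the look: "A non-binding futility analysis is planned for each cohort when 12 subjects have at least 2 evaluable tumor response evaluations after starting therapy". It names no study part, dose level or regimen. It adds "Reported probabilities are based on exact calculations" and then gives the figures. For the uninteresting rate: "There is a 54% chance that a result of 0 responses is observed when the true response rate is 5" percent. For the 15% target: "the chance of 0 responses is 14%, 1 response 30%, and 1 or more responses 96" percent. The interpretation offered is that "observing 1 or more responses at the interim analysis would be supportive of further enrollment". Section 10.1 says the look may affect how many subjects Part B finally enrolls.

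Section 10.1 is more specific about the sample behind the efficacy benchmark. Once Part B is enrolled, "each disease-specific cohort will have approximately 25 subjects treated at the RP2D, including the Part A and Part B subjects". Part A is sized by "assuming 3 dose-escalation cohorts of 6 subjects each (18 subjects) across 8 disease cohorts".

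Three other places bear on who the 12 could be:

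- Section 3.1 makes Part A and Part B two parts of each disease cohort.
- Section 3.1.1 (Table 3-1) plans 0.2, 0.3 and 0.4 mg/kg every 6 weeks, and allows extra subjects at a level already found tolerable.
- Section 3.1.2 lets Part B study the maximum tolerated dose (MTD) or something lower, possibly more than one regimen.

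**The concern.** The probabilities in Section 10.3.6 describe 12 subjects who share one response rate. They inform a decision about Part B, so they are useful only if that rate belongs to the regimen Part B would expand. The benchmark sample in Section 10.1 is tied to the RP2D. The interim sample is tied to nothing beyond the cohort, and a cohort includes the dose-escalation subjects.

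A result of 0 in 12 could then partly reflect lower doses rather than the regimen under consideration. Responses at another dose could equally carry an inactive regimen past the look. Two statisticians applying the text could also choose different sets of 12 for the same cohort and report opposite signals.

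**Working it through.** **Inputs.** From Section 10.3.6: n = 12, rates of 5% and 15%, exact calculation. From Section 10.1: up to 18 Part A subjects per disease, 6 at each of three levels. From Section 3.1.1: at least 6 subjects at the putative MTD or RP2D. Not in the documents: response rates by dose in these tumors. Rates of 0% to 20% are assumed below.

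**Step 1: reproduce the plan's figures (binomial, n = 12).**

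| Quantity | Formula | Result | Stated |
|---|---|---|---|
| P(0) at 5% | 0.95^12 | 54.0% | 54% |
| P(0) at 15% | 0.85^12 | 14.2% | 14% |
| P(1) at 15% | 12 × 0.15 × 0.85^11 | 30.1% | 30% |
| P(1 or more) at 15% | 1 − 0.85^12 | 85.8% | 96% |

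The first three reproduce, which confirms the single-rate model. The fourth does not, and the stated 14% and 96% for complementary outcomes sum to 110%. That is a separate slip in the same paragraph; the present point does not rest on it.

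**Step 2: how many of the 12 could be off the expanded regimen.** At the planned maximum, 18 − 6 = 12 Part A subjects sit at levels other than the chosen one. If the middle level is chosen, up to 6 are below it and up to 6 above. If the top level is chosen, up to 12 are below. These are ceilings. A level cleared with no dose-limiting toxicity in 3 subjects need hold only 3, and each counted subject needs two evaluable assessments. One other level, filled with 3 or 6 subjects, is therefore the case to examine.

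**Step 3: chance of 0 responses when the expanded regimen truly has a 15% rate.** With k of the 12 off that regimen at an assumed rate p:

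P(0) = (1 − p)^k × 0.85^(12 − k)

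For k = 3 the second factor is 0.85^9 = 0.2316; for k = 6 it is 0.85^6 = 0.3771.

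| Assumed p off regimen | k = 3 | k = 6 |
|---|---|---|
| 0% | 23.2% | 37.7% |
| 5% | 0.95^3 × 0.2316 = 19.9% | 0.95^6 × 0.3771 = 27.7% |
| 10% | 16.9% | 20.0% |
| 15% | 14.2% | 14.2% |
| 20% | 11.9% | 9.9% |

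**Step 4: the opposite error.** If the expanded regimen has a 5% rate and the k others are assumed to respond at 15%, P(0) = 0.85^k × 0.95^(12 − k). This falls from the stated 54.0% (k = 0) to 38.7% (k = 3) and 27.7% (k = 6), so an inactive regimen would be flagged less often.

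**The case against.** The case against a stronger finding is good, and most of it stands.

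- **The text is silent.** A reader might infer that the plan deliberately counts subjects below the RP2D. No section says so. The word cohort also denotes a 3+3 dose group and a Part B expansion group. Section 10.1 links the look to Part B, and the synopsis says data are analyzed by disease, cohort and dose regimen. These point toward a regimen-specific reading, but none of them defines the 12.
- **A reader might infer that the 14% is wrong.** It is right for 12 subjects who share a 15% rate, and equal rates across doses leave it unchanged. Section 3.2.1 describes the Part A doses as expected to be active, and the small cell lung cancer activity cited in Section 1.2 was seen at 0.2–0.4 mg/kg. A 0% rate at the lower levels is therefore the extreme assumption. Subjects above the chosen level could push the chance below 14%.
- **A reader might infer a false-stop rate of 28% or more.** The look is non-binding, is read alongside safety data and has no written stopping rule. The trial is open-label, so those reviewing it know each subject's dose.
- **The extreme mixtures are special cases.** With the middle level chosen, 9 or 12 subjects below it would require extra enrollment at the lower level. Section 3.1.1 also lets Part B open for all cohorts once three have cleared 0.3 or 0.4 mg/kg, so some cohorts may have few lower-dose subjects.
- **A reader might infer that the interim and final analyses use different populations by design.** The 25 at the RP2D is a sample-size projection, and the response-rate analysis in Section 10.3.4 is itself reported by disease and cohort without an RP2D limit.
- **Section 10 defers detail to a statistical analysis plan.** No separate text of it is in the document reviewed, and the 12 may be defined there.

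What remains is that Section 10.3.6 gives exact probabilities for a group it does not define, and the ordinary meaning of a disease cohort in Section 3.1 admits subjects on other doses.

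**Conclusion.** The point holds as a should-fix. The rule as written can be met partly by Part A subjects off the regimen being expanded and, if Part A fills to its planned size with enough evaluable subjects, wholly by them. In that case the 14% need not describe that regimen. With 3 to 6 such subjects at an assumed 5% rate, the chance of 0 responses is about 20% to 28%. Over assumed rates of 0% to 20% it runs from 38% down to 10%, with no change from 14% when the rates are equal. These figures rest on assumed rates and an assumed mix; the documents supply neither. They show that the look's operating characteristics are undefined until its population is fixed. They do not show that an effective regimen would be stopped at any particular frequency.

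**What to change.** In Section 10.3.6, reword the trigger along these lines: *the analysis is done in each disease cohort when 12 subjects treated at the regimen being expanded (Part A subjects on that regimen plus Part B subjects) meet the two-evaluation condition; if Part B studies more than one regimen, it is done separately by regimen; responses at other dose levels are shown as supportive information only.* The stated 14% and 54% then apply to the regimen in question, and the interim sample matches the basis used in Section 10.1. The same edit should correct the 96% to 86%.

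The main cost is timing. If 6 Part A subjects received the expanded regimen and are evaluable, 12 − 6 = 6 Part B subjects are needed; if none did, 12 of the approximately 19 planned for a disease-specific cohort are needed. Where a cohort's Part B is split between two regimens (about 9 or 10 subjects each), a regimen with few Part A subjects may not reach 12. The text should say what is shown in that case.

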### **6.3.7 Disease Assessment**

- Disease assessment consists of CT scans of the chest, abdomen, and pelvis (and neck if indicated; [Section 7.3](#)). Tumor response will be assessed every 6 weeks counting from Cycle 1 Day 1, preferably before each dosing if possible, until 24 weeks, then every 12 weeks, thereafter.
- MRI of the brain – if clinically indicated (e.g., if CNS progression has been documented previously). CT of the brain with intravenous contrast may be substituted at the discretion of the Investigator. CNS lesion will be assessed every 6 weeks counting from Cycle 1 Day 1, preferably before each dosing if possible, until 24 weeks, then every 12 weeks, thereafter.
- Prostate cancer subjects only: 99 mTc Bone Scintigraphy, will be assessed every 6 weeks counting from Cycle 1 Day 1, preferably before each dosing if possible, until 24 weeks, then every 12 weeks, thereafter ([Section 7.3](#)).

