### **7.3 Radiographic Response/Efficacy Assessments**

Radiographic evaluations at protocol-specified time points include:

- CT scans of the chest, abdomen and pelvis (scans of the neck must also be obtained for MTC and/or if there is documented or suspected involvement in this region)
- MRI of the brain, if indicated. CT of the brain with intravenous contrast may be substituted at the discretion of the Investigator.
- Whole-body technetium-99m (99mTc) bone scintigraphy (prostate cancer subjects only)

Diagnostic quality, spiral CT scans are recommended; other methods may be used if performed consistently throughout the study for each individual subject. Positron emission tomography (PET) and/or octreotide/somatostatin scans may be used in an ancillary manner; however, no decisions relating to PD may be made based on PET or octreotide/somatostatin scans alone. Clinical response will be determined by the Investigator at each assessment according to RECIST v1.1 ([Appendix 13.6](#); [Eisenhauer 2009](#)), and/or for prostate cancer subjects, PCWG3 criteria ([Appendix 13.7](#)).

For tumors to be assigned a status of responder (PR or CR), changes in tumor measurements must be confirmed by repeat assessments performed no less than 4 weeks, but preferably not more than 6 weeks, after the criteria for response are first met; i.e., two consecutive assessments of PR or CR are required. In instances where a follow-up visit is not otherwise scheduled to occur for more than 6 weeks, repeat radiographic disease assessments should be conducted at least 4 but not more than 6 weeks after the criteria for response are first met, in order to confirm response, whether or not a formal follow-up visit is conducted at the same time.

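### If responses must be confirmed, the futility look's 14% chance of 0 responses in 12 makes no allowance for a PR or CR first seen at the second scan

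*Combined protocol and SAP*

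**What the plan says.** Section 10.3.6 (Futility Analysis) describes a non-binding look "planned for each cohort when 12 subjects have at least 2 evaluable tumor response evaluations after starting therapy". Its purpose is an early indication of activity, to be weighed with cohort safety data. It says "Reported probabilities are based on exact calculations" and gives these figures, all in per cent:

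- at a 5% rate: "There is a 54% chance that a result of 0 responses is observed when the true response rate is 5";
- at a 15% rate: "When the response rate in the population is the target rate of interest (15%); the chance of 0 responses is 14", followed by "1 response 30%, and 1 or more responses 96".

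It concludes that "observing 1 or more responses at the interim analysis would be supportive of further enrollment". It does not say whether a response at this look must be confirmed.

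Section 7.3 does set a confirmation rule. A subject becomes a responder only when PR or CR is repeated at least 4 weeks later: "i.e., two consecutive assessments of PR or CR are required". Footnote 23 to the Schedule of Assessments (Appendix 13.1) points back to this rule. Section 10.3.4 defines best overall response as the highest one recorded up to end of treatment, and does not mention confirmation.

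On timing, Section 6.3.7 says "Tumor response will be assessed every 6 weeks counting from Cycle 1 Day 1", up to Week 24. The first two assessments therefore fall at about Weeks 6 and 12.

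**The concern.** Under Section 7.3, a subject with exactly two scans can be a responder only if PR or CR was already present at the first. A PR first seen at Week 12 needs a third scan, at about Week 18, yet the look can be triggered without it. The 14% gives each of the 12 subjects the full 15% rate, as if nothing were pending or still to come.

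A single response is what separates a supportive result from an unsupportive one, so one pending PR can change how a cohort reads. Because Section 10.3.6 does not define an interim response, two analysts could follow the text and report 0 of 12 and 1 of 12 for the same cohort. Section 10.1 says the look may affect how many subjects Part B enrols.

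**Working it through.** **Inputs from the plan.** n = 12; response rates of 15% and 5% (Section 10.3.6); two consecutive assessments for a response (Section 7.3); scans every 6 weeks (Section 6.3.7).

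**Inputs not in the plan.** f is the share of eventual confirmed responders already countable at the look. d is the share of subjects who never reach two evaluable assessments. Both are assumptions, shown as ranges.

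**Step 1: the plan's own figures (exact binomial, n = 12).**

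| Quantity | Formula | Result | Stated |
|---|---|---|---|
| P(0), rate 5% | 0.95^12 | 54.0% | 54% |
| P(0), rate 15% | 0.85^12 | 14.2% | 14% |
| P(exactly 1), rate 15% | 12 × 0.15 × 0.85^11 | 30.1% | 30% |
| P(1 or more), rate 15% | 1 − 0.85^12 | 85.8% | 96% |

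The first three reproduce. The fourth does not. It also contradicts the stated 14%: the two are complements, yet 14% + 96% = 110%.

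**Step 2: confirmation required, all 12 with exactly two scans.** P(0) = (1 − 0.15f)^12.

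- f = 1: 0.85^12 = 14.2%
- f = 0.9: 0.865^12 = 17.5%
- f = 0.8: 0.88^12 = 21.6%
- f = 0.5: 0.925^12 = 39.2%

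**Step 3: six of the 12 followed long enough for full credit.** The trigger sets a minimum of two assessments, so subjects enrolled earlier may have more. P(0) = 0.85^6 × (1 − 0.15f)^6.

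- f = 0.8: 0.85^6 × 0.88^6 = 17.5%
- f = 0.5: 0.85^6 × 0.925^6 = 23.6%

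**Step 4: the opposing effect.** Requiring two evaluable assessments can leave out subjects who progress or die early. If a share d is lost this way and all are non-responders, the rate among those counted rises. With all 12 at exactly two scans, P(0) = (1 − 0.15f/(1 − d))^12.

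- d = 20%, f = 1: 0.8125^12 = 8.3%
- d = 20%, f = 0.8: 0.85^12 = 14.2%
- d = 20%, f = 0.5: 0.90625^12 = 30.7%

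At d = 20% and f = 0.8 the two effects cancel exactly.

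**The case against.** A reader might infer that the 14% is a miscalculation, or that it is simply too low. The documents support neither reading.

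- **The arithmetic is right.** Step 1 reproduces it.
- **Confirmation at the look is not stated.** Section 10.3.6 asks for a preliminary signal, Section 10.3.4 does not mention confirmation, and the 15% target is never called a confirmed rate. If unconfirmed PR or CR counts, a response first seen at the second scan counts too, and only responses first seen later are missed.
- **Follow-up will often exceed two scans.** Section 10.1 plans about 25 subjects per disease-specific cohort at the recommended dose, about 19 of them from Part B, so about 6 come from Part A. Section 10.3.6 does not say whether the 12 include them. If they do, up to half could have longer follow-up, as in Step 3.
- **The direction is not fixed.** Step 4 shows that the two-assessment requirement can cancel or reverse the effect.
- **The rule is non-binding.** Zero responses does not by itself close a cohort, and nothing prevents reviewers from considering a pending PR.

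All of this stands, and it makes the point conditional. It does not remove it. Section 7.3 is the only text that says when a subject becomes a responder, and under that rule the 14% omits pending responses. If unconfirmed responses are meant instead, the look uses a different definition from Section 7.3 with the same 15% and 5% benchmarks, and does not say so. Section 10 leaves further detail to the SAP, but the documents contain no SAP text defining an interim response.

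**Conclusion.** The point holds conditionally, as a gap in the definition of the look and its operating characteristics. If the Section 7.3 rule governs, 14% is the chance of 0 of 12 at a 15% rate only when every eventual responder is already countable.

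Before any selection effect, the chance is 17.5% to 39.2% for f from 0.9 down to 0.5 with exactly two scans each, and 17.5% to 23.6% for f from 0.8 down to 0.5 with half the subjects fully followed. These sizes rest on f, for which the documents give no figure. Loss of early progressors could bring the chance back to 14% or below. The change is worth making because it is small and removes one route to a false futility signal.

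The 96% in the same sentence is a definite error and needs no assumption: the value is 85.8%.

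**What to change.** In Section 10.3.6:

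1. State that any PR or CR, confirmed or awaiting confirmation, counts as a response at the futility look, and that 0 of 12 is not declared while a first PR or CR awaits its confirmatory scan. Keep confirmed response for the final ORR.
2. Label the 14% and 54% as binomial figures that assume the 15% and 5% rates apply to that interim definition. Responses first seen after the second scan can still be missed.
3. Correct the chance of one or more responses at a 15% rate from 96% to 86%.

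The edit takes a few sentences and no extra data. The cost is that an inactive cohort is somewhat less likely to be flagged. As an illustration, if a 5% confirmed rate corresponded to a 7% rate including unconfirmed responses (an assumption), the chance of 0 of 12 would fall from 54% to 0.93^12, about 42%. A non-binding look can reasonably accept that, but the section should say so.
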